### **3.3 Study Endpoints**

#### **3.3.1 Primary Endpoints**

- The occurrence and severity of treatment emergent AEs.

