Clinically significant abnormal laboratory or other examination (e.g., ECG) findings that are detected during the study or are present at Screening and significantly worsen during the study should be reported as AEs, as described below. The Investigator will exercise his or her medical and scientific judgment in deciding whether an abnormal laboratory finding or other abnormal assessment is clinically significant. Clinically significant abnormal laboratory values occurring during the clinical study will be followed until repeat tests return to normal, stabilize, or are no longer clinically significant. Abnormal test results that are determined to be an error should not be reported as an AE. Laboratory abnormalities or other abnormal clinical findings (e.g., ECG abnormalities) should be reported as an AE if any of the following are applicable:

- If an intervention is required as a result of the abnormality
- If action is required to be taken with the study drug as a result of the abnormality
- Based on the clinical judgment of the Investigator

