  - If the subject states that he or she is not ready to stand, the subject will be allowed to sit as positioned for one additional minute and will be asked again if they are ready to stand. The subject will proceed to stand. After standing for 2 minutes, one measurement will be taken for blood pressure and heart rate.
  - If the individual is still unable to stand, vital signs will be measured while the subject is in an upright seated position.

Orthostatic hypotension will be defined as a reduction in SBP of 20 mmHg or more, and/or a reduction in DBP of 10 mmHg or more, for the standing measurement compared to the supine or semi-supine measurement. If orthostatic hypotension is suspected, the measurement process may be repeated at the Investigator's discretion. Any confirmed orthostatic hypotension or clinically significant measurements that are associated with clinical symptoms will be recorded as adverse events.

If routine VS and orthostatic VS coincide at the same time points, the same values for routine VS (blood pressure and heart rate) during the supine or semi-supine position should be recorded in the CRFs as the same values of the start of orthostatic VS in the supine or semi-supine position.

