#### 6.1.8. Derived Variables

- **TETRAS-PS Total score** = sum of the 16 individual item scores (only the maximum of the item 5 lower limb tremor scores will be counted), with a maximum total score of 64. There will be no missing value imputation performed.
- **TETRAS-PS Upper Limb Subscale score** = sum of the item 4, item 6, item 7 and item 8 scores (forward outstretched postural tremor, lateral “wing beating” postural tremor, kinetic tremor, Archimedes spirals, and dot approximation task from both sides of the body, as well as handwriting), with a maximum total score of 44. There will be no missing value imputation performed.
- **TETRAS-PS Upper Limb Tremor (Item 4) Total score** = sum of the 6 individual scores under item 4 scores (forward outstretched postural tremor, lateral “wing beating”

postural tremor, and kinetic tremor scores for left and right hand, respectively) from both sides of the body, with a maximum total score of 24. There will be no missing value imputation performed.

Commercially Confidential Information

- **Kinesia Upper Limb Tremor score** = sum of the scores from the extended arms posture, wing-beating posture, and kinetic “finger-to-chin” wearable sensor maneuvers from both sides of the body, with a maximum total score of 24. There will be no missing value imputation performed.
- **Change from baseline** = value at current time point – value at baseline.
  - For calculation of change from baseline to Day 14 for discontinued subjects their assessment value at the early termination (ET) visit should be used
- **Percent change from baseline** = (change from baseline / baseline) \* 100. If both baseline and change from baseline are 0 then percent change from baseline will be set to 0.
- **Study day** = number of days relative to the first dose date of study drug and will be calculated using the following formulas:  
For pre-dose: study day= Start Date/ Stop Date – first dose date;  
For post-dose: study day= Start Date/ Stop Date – first dose date + 1.
- **TEAE (treatment-emergent AE)** = any AE with an onset date/time after the first dose of treatment. If an AE was present at baseline and worsened on or after the first dose of treatment it will be considered a TEAE.
- **Orthostatic hypotension** is defined as a reduction in SBP of 20 mmHg or more, and/or a reduction in DBP of 10 mmHg or more, for the standing measurement compared to the supine or semi-supine measurement.

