### 9.3. Vital Signs

Descriptive summaries of observed values and changes from baseline will be calculated for supine systolic blood pressure (SBP), standing SBP, supine diastolic blood pressure (DBP), standing DBP, supine heart rate (HR), standing HR, respiration rate, and oral temperature by study visit for the Safety Population overall and by cohort. Shifts from baseline for SBP, DBP, and HR values below, within, or above the normal range will be provided by study visit for the Safety Population overall and by cohort. Vital sign parameters outside the normal range will be flagged in the listings. The mean change from baseline in each parameter will also be plotted by study visit. Abnormal vital signs are as follows:

Commercially Confidential Information

- SBP >140 mmHg
- SBP <90 mmHg
- DBP >90 mmHg
- DBP <60 mmHg
- HR >100 bpm
- HR <60 bpm
- Respiration rate >20 breaths/min
- Respiration rate <12 breaths/min
- Oral temperature >99.1 °F/37.2 °C
- Oral temperature <97.8 °F/36.5 °C

Orthostatic vital signs (blood pressure and heart rate) will also be summarized by position and study visit and by cohort. During the Pre-dose visit, baseline orthostatic vital signs will include 3 separate measurements and the average of the 3 baseline orthostatic vital signs measurements will be used for comparison to all post-treatment measurements. The average HR, SBP, and DBP will be presented in the pre-dose baseline summaries and each of the individual measurements will be listed for that study visit.

Orthostatic hypotension will be defined as a reduction in systolic blood pressure of 20 mmHg or more and/or a reduction in diastolic blood pressure of 10 mmHg or more, for the standing measurement compared to the supine or semi-supine measurement. The frequency and percentage of subjects with orthostatic hypotension will also be presented by cohort. Any confirmed orthostatic hypotension or clinically significant measurements that are associated with clinical symptoms will be recorded as AEs. Orthostatic vital signs parameters outside the ranges specified above will be flagged in the listings.

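### Whether an asymptomatic orthostatic drop counts as a TEAE depends partly on site practice, and the measured-hypotension table leaves out Day 1

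*Protocol*

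**What the plan says.** **Definition.** Protocol 7.10: "Orthostatic hypotension will be defined as a reduction in SBP of 20 mmHg or more", and/or a diastolic fall of at least 10 mmHg, standing against supine or semi-supine. SAP 6.1.8 agrees: OH "is defined as a reduction in SBP of 20 mmHg or more, and/or a reduction in DBP of 10 mmHg or more". SAP 9.3 repeats the threshold. None of these asks for a second reading or for symptoms. The procedure in 7.10 takes one supine reading and one standing reading; for a subject who needs extra time before standing it says "After standing for 2 minutes, one measurement will be taken for blood pressure and heart rate".

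**Repeat.** Protocol 7.10: "If orthostatic hypotension is suspected, the measurement process may be repeated at the Investigator's discretion". It gives no trigger value, number of repeats or timing.

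**Recording as an AE.** Protocol 7.10: "Any confirmed orthostatic hypotension or clinically significant measurements that are associated with clinical symptoms will be recorded as adverse events". SAP 9.3 carries the sentence over: "Any confirmed orthostatic hypotension or clinically significant measurements that are associated with clinical symptoms will be recorded as AEs".

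**General AE rule.** Protocol 7.1 has abnormal clinical findings reported as AEs if they need an intervention, if they lead to action with study drug, or "Based on the clinical judgment of the Investigator".

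**Endpoint.** Protocol 3.3.1 gives the primary endpoint as "The occurrence and severity of treatment emergent AEs".

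**Outputs.** SAP 9.3 plans the number and percentage of subjects with OH by cohort. The shell for this, Table 14.3.6.1.6, has blocks for Baseline, Day 7, Day 14 and Day 21, each with one systolic row and one diastolic row. Listing 16.2.8.3.2 has an OH column, and Listing 16.2.7 lists all AEs.

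**The concern.** The definition rests on one comparison, while the recording rule rests on a word that the definition does not contain. Two sites could see the same asymptomatic fall. One repeats the reading, reproduces the fall and records an AE; the other does not repeat it and may record nothing. Two sites that both repeat could still differ, if one takes the symptom clause to cover OH and the other does not.

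The primary endpoint inherits this variation. The protocol treats OH as safety-relevant even without symptoms: exclusion criterion 19 bars anyone who has ever had it, symptomatic or not. With about 30 subjects at up to 15 sites, the average could be as low as 30/15 = 2 subjects per site, so differences in local practice have little chance to average out. TEAEs are also shown by cohort, and the cohorts differ in dosing interval on Days 1, 7 and 14. A cohort difference in recorded OH could then reflect repeat practice as well as drug.

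**Working it through.** The plan states no figure for OH, so there is nothing to reproduce. The check compares the texts, then the outputs.

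**1. Possible readings of the recording sentence.** *Confirmed* may mean that the reading meets the definition just given, or that a repeat reproduced it. The symptom clause may cover only the clinically significant measurements, or both nouns. That gives four rules for OH:

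| Reading | *Confirmed* means | Symptoms needed for OH | OH recorded when |
|---|---|---|---|
| A | meets threshold | no | every threshold drop |
| B | meets threshold | yes | symptomatic threshold drops |
| C | reproduced on repeat | no | drops that were repeated and reproduced |
| D | reproduced on repeat | yes | drops repeated, reproduced and symptomatic |

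An asymptomatic, unrepeated drop is an AE under A and not under B, C or D. An asymptomatic drop that was repeated and reproduced is an AE under A and C and not under B or D. Nothing in either document selects among the four.

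**2. Scheduled readings after first dose (Protocol 7.10).** Day 1: 2. Day 7: 1. Day 14: 1. Follow-up: 1. Total 2 + 1 + 1 + 1 = 5. Day 1 holds 2/5 of these, and 2 of the 4 taken on dosing days. This is the current protocol's schedule; Cohort-1 was enrolled under Amendment 1, whose schedule is not in the documents.

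**3. What the OH table would show.** The shell of Table 14.3.6.1.6 covers Days 7, 14 and 21, so 3 of the 5 readings. Table 14.3.6.1.5, which uses the same thresholds plus heart rate, also starts at Day 7. Day 1 does appear in the visit list for Table 14.3.6.1.3, but that table summarises each position separately and does not count subjects with OH. Because the definition is and/or, the two rows per visit do not give the number of subjects with OH: if a subjects meet the systolic limit and b the diastolic limit, the count lies anywhere from max(a, b) to a + b. No row counts subjects with OH at any post-dose reading, and no table shown relates measured OH to recorded OH.

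**4. Illustration only, on assumed rates.** Let p be the chance that a reading crosses the threshold, r the chance that the site repeats it, c the chance that the repeat also crosses, and s the share with symptoms. The documents give none of these. Treating 5 readings as independent, expected subjects of 30 with a recorded OH event through the *confirmed* limb are 30 × [1 − (1 − q)^5], where q = p (A), ps (B), prc (C) or prcs (D). At p = 0.05:

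- A: 30 × (1 − 0.95^5) = 6.8
- B, s = 0.1 to 0.3: q = 0.005 to 0.015, giving 0.7 to 2.2
- C, c = 0.3 to 0.8: 0 if r = 0; 1.1 to 2.9 if r = 0.5; 2.2 to 5.5 if r = 1
- D, c = 0.5, s = 0.1 to 0.3: 0.2 to 0.6 if r = 0.5; 0.4 to 1.1 if r = 1

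Reading A gives 2.9 at p = 0.02 and 12.3 at p = 0.10, against 0 under C or D with no repeats. The span is set almost entirely by the assumptions, so it does not estimate the effect.

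**The case against.** The strongest reply has four parts.

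*Confirmed need not mean repeated.* It can mean that the reading meets the definition two sentences before, and then definition and recording rule agree. This is a fair reading, and the link to the repeat is an inference. But the word follows directly on a sentence about suspected OH and an optional repeat, so a site could reasonably take it either way. The scope of the symptom clause stays open on both readings.

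*An AE does not require confirmation.* A reader might infer that OH becomes an AE only if confirmed, or that an unrepeated asymptomatic drop can never be one. The documents do not support that. The sentence has a second limb for clinically significant measurements, and Protocol 7.1 lets the investigator report any abnormal finding on judgement. Those routes are discretionary too, so they leave the dependence on site practice in place.

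*Measured OH is reported separately.* A reader might also infer that recorded and measured OH cannot be reconciled. They can, subject by subject, from Listings 16.2.7 and 16.2.8.3.2. The gap is in the summary tables.

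*The study is descriptive.* It has one arm and about 30 subjects, no between-site comparison is planned, and investigator judgement governs laboratory and ECG findings as well. This limits the consequence. It does not explain why an event with a numerical definition has a recording rule that can be read in four ways.

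**Conclusion.** The point holds in a limited form. OH is defined by one threshold comparison, but its recording as an AE turns on an undefined term, an optional repeat and a symptom clause of unclear scope. Whether an asymptomatic threshold drop counts in the primary TEAE endpoint is therefore partly a matter of site practice. The measured-OH table only partly makes up for this: as its shell stands, an unrepeated asymptomatic drop on Day 1 can be absent from both the TEAE tables and the OH table, and would then be found only in a listing.

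The size is unknown. A reader might be tempted to put a multiple on it. For example, at an assumed 3% per reading, 1 − 0.97^5 = 14.1% of subjects have a drop; if a quarter of drops became AEs, 1 − (1 − 0.0075)^5 = 3.7% would have an OH AE, nearly a fourfold difference. That ratio only returns the assumed quarter, and its comparator, recording every drop, is a rule that the sentence does not plainly state. It should not be relied on. The conclusion rests on the wording and the table shells, and needs no rate. It warrants a correction but does not undermine the safety analysis as a whole.

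**What to change.** **Protocol 7.10 and SAP 9.3.** Reconcile the definition, the repeat and the recording sentence so that AE recording follows one stated trigger that is not discretionary. If the trigger is a repeat, state when it must be done and what result confirms OH. If it is the defined reading, drop *confirmed*. Write the two limbs as separate conditions, so that it is explicit whether symptoms are required for threshold OH. Which rule to adopt is for the sponsor.

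**SAP 9.3 and Table 14.3.6.1.6.** Add both Day 1 post-dose readings. Add a row for subjects meeting the and/or definition at any post-dose reading, cross-classified by OH recorded as a TEAE (yes/no), overall and by cohort. Name in advance the preferred terms that count as an OH TEAE.

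**Cost.** Wording changes in two documents, a few more repeat readings or mild AE records depending on the rule chosen, and one table block plus one row from data already collected. If data collection is complete, the protocol change can no longer help, but the SAP change still lets recorded OH be read against measured OH.

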### **7.11 Clinical Laboratory Evaluations**

A list of clinical laboratory tests to be performed is in [Appendix B](#). See [Table 2](#), SOA in [Appendix A](#) for the timing and frequency.

The Investigator must review the laboratory report, document this review, and record any clinically relevant changes occurring during the study in the AE section of the eCRF. The laboratory reports must be filed with the source documents. Clinically significant abnormal laboratory findings are those which are not associated with the underlying disease, unless judged by the Investigator to be more severe than expected for the subject's condition.

All laboratory tests with values considered clinically significantly abnormal during participation in the study or within 30 days after the last dose of study intervention should be repeated until the values return to normal or baseline or are no longer considered clinically significant by the Investigator or Medical Monitor.

- If such values do not return to normal/baseline within a period of time judged reasonable by the Investigator, the etiology should be identified and the CRO notified.
- All protocol-required laboratory assessments, as defined in [Appendix B](#), must be conducted in accordance with the laboratory manual and the SOA ([Table 2](#)).
- If laboratory values from non-protocol specified laboratory assessments performed at the institution's local laboratory require a change in the subject's management or are considered clinically significant by the Investigator (e.g., SAE or AE or dose modification), then the results must be recorded as an AE in the eCRF for AEs and also the paper form if an SAE.
- On Days 1, 7, 14 all clinical laboratory samples should be collected after the TETRAS-PS assessment

### **7.12 Columbia Suicide Severity Rating Scale (C-SSRS)**

The C-SSRS is a questionnaire that prospectively assesses Suicidal Ideation and Suicidal Behavior. The C-SSRS, which uses a semi-structured interview to probe subject responses, will be administered by an individual who has received training and certification in its administration. At the Baseline/Pre-dose visit, the "baseline" version of the C-SSRS will be administered. This version assesses Suicidal Ideation and Suicidal Behavior during the subject's lifetime and during

a predefined period. At the Day 21 visit (and the Early Termination visit for subjects withdrawing early), the “since last visit” version will be administered.

## 8 EFFICACY ASSESSMENTS

### 8.1 Rating Scales

The treatment effect will be evaluated by means of the TETRAS-PS (Version 3.1), which is a validated scale that has been used in recently conducted clinical trials in subjects with ET ([Elble, 2012](#)). It provides an accurate reflection of the clinical response to treatment on the amplitude of tremor over multiple bodily locations and over time.

The TETRAS assessments at Screening, Baseline/Pre-dose, Days 1, 7, 14, and Follow-up visit (Day 21) will be administered by a certified rater. TETRAS raters at each site must demonstrate expertise in the administration of the TETRAS according to criteria preset by independent central rating experts. The TETRAS raters at each site can be the Principal Investigator or a staff member delegated as a rater by the Principal Investigator. Each site must make every effort, to the extent that is possible, to ensure availability of a primary rater and a backup rater to perform all TETRAS assessments on the same subjects throughout the study duration.

The TETRAS-PS assessments at the Screening visit, Baseline/Pre-dose, Days 1, 7, 14, and 21 clinic visits will be recorded using videography for centralized evaluation and rating by independent blinded central raters (neurologists) with expertise in the assessment of ET.

Commercially Confidential Information

On Screening and Baseline/Pre-dose visits: TETRAS-PS, Commercially Confidential Information are performed.

On Day 1: The TETRAS-PS will be administered 2 to 4 hours following the second in-clinic dose.

On Day 7: the TETRAS-PS, Commercially Confidential Information will be performed 2 to 4 hours following the in-clinic dose.

On Day 14: the TETRAS-PS, Commercially Confidential Information will be performed 2 to 4 hours following the in-clinic dose. Commercially Confidential Information

At Follow up visit (Day 21): the TETRAS-PS, Commercially Confidential Information are performed once any time during the visit.

Commercially Confidential Information

## 8.2 Wearable Sensor

In addition to the assessment of efficacy via rating scales, treatment effect will be evaluated by measuring tremor with a sensor worn on the upper limb (index finger). These assessments will be conducted during the clinic visits and optionally at-home.

### 8.2.1 In-Clinic Assessment

The wearable sensor measurements of upper limb tremor assessments will be completed in the clinic once at any time during the Screening visit and at two different times during the Baseline/Pre-dose site visit.

During the site visit on Day 1 the wearable sensor measurements of upper limb tremor will be captured once, 2 to 4 hours following the second in-clinic dose.

During the site visit on Days 7 and 14, the wearable sensor measurements of upper limb tremor will be captured once, 2 to 4 hours following the in-clinic dose.

During the Follow-up visit (Day 21), the wearable sensor measurements of upper limb tremor will be completed at any time during the visit.

In-clinic assessments will be obtained during the performance of 4 maneuvers:

1. extended arms posture,
2. wing-beating posture,
3. kinetic “finger-to-chin” movement, and
4. arm on table posture.

These assessments will be performed twice, once with the sensor on the left index finger and once with the sensor on the right index finger.

In addition, the subject will wear the sensor on the index finger of each hand while performing 3 activities of daily living:

1. pouring from a cup,
2. drinking from a cup, and
3. eating with a spoon

Commercially Confidential Information

Commercially Confidential Information

Commercially Confidential Information

Commercially Confidential Information

## 11 STATISTICS

### 11.1 Analysis Populations

For purposes of analysis, the following populations are defined:

Safety population: All enrolled subjects who take at least 1 dose of study intervention.

- Full Analysis Set (FAS): FAS consists of subjects in the safety population who had at least 1 post-baseline assessment of both TETRAS-PS CCI . FAS will be used to summarize all efficacy data.

Commercially Confidential Information

- Exposed Population (EP): The exposed population includes all subjects in the Safety population who are at least 90% compliant with study treatment

Commercially Confidential Information

Selected efficacy analyses will be repeated in this population if this population differs from FAS.

### 11.2 Statistical Methods

The statistical analysis plan (SAP) will be developed and finalized before database lock and will describe the subject populations to be included in the analyses, and procedures for accounting for missing, unused, and spurious data. This section is a summary of the planned statistical analyses of the primary and secondary endpoints.

#### 11.2.1 Analysis of Primary (Safety) Endpoint Data

- Vital sign parameters outside the normal range will be listed and flagged for review.
- Orthostatic vital signs parameters for blood pressure outside the ranges specified in [Section 7.10](#) below will be listed and flagged for review.
- Descriptive statistics of absolute and change from Baseline (pre-dose) SBP, DBP, pulse rate, respiratory rate, and oral temperature at each timepoint, will be tabulated. The mean change from Baseline data will also be plotted across time.
- Twelve-lead ECG parameters will be listed with any values outside the normal range flagged. Descriptive statistics of absolute and change from Baseline (pre-dose) heart rate, PR, QRS, QT, and QTcF intervals at each timepoint, will be tabulated. The mean change from Baseline data will also be plotted across time.
- In addition, frequencies of QTcF data will be calculated according to the following categories:

For absolute values

- QTcF >450 msec (males) and >470 msec (females)
- QTcF >480 msec
- QTcF >500 msec

For change from Baseline

- QTcF increase >30 msec
- QTcF increase >60 msec

